## Table 7. Randomized treatment non-responders and estimated number followed at 6, 12 and 24 months

Randomized treatment	Non-responders at 3 months	Followed to 6 months	Followed to 12 months	Followed to 24 months
BIO	17	17	15	13
INJ	63	60	53	45

# Table 8. 95% Confidence intervals for observed responder (or non-responder) percentages of 50-90% and treatment-order combination group sizes of 5-50 participants

Number of	Responder (or non-responder) percentage				
participants	50%	60%	70%	80%	90%
5		23-88%		38-96%	
10	24-76%	31-83%	40-89%	49-94%	60-98%
20	30-70%	39-78%	48-85%	58-92%	70-97%
30	33-67%	42-75%	52-83%	63-90%	74-97%
40	35-65%	45-74%	55-82%	65-90%	77-96%
50	37-63%	46-72%	56-81%	67-89%	79-96%

#### 5.4 Estimated patient flow for this study

Figure 3 shows the estimated flow of patients through this study and identifies our assumptions regarding attrition. We estimate we will need to screen 855 patients because 2/3 will be ineligible or unwilling to be randomized. This leaves 285 to be recruited into the EMM protocol. Based on the Heymen study, we assume

15% attrition during this treatment phase and also assume that 20% (n=57) will be responders to EMM and therefore not eligible for randomization. This will leave 194 to be randomized (97 per group).

Figure 3 shows that we expect 78 from the BIO group to complete the 3-month assessment after allowing for attrition of 20% and we expect 92 from the INJ group to complete the 3-month assessment. (We assume attrition will be no greater than 5% for the INJ group because this is a low-burden treatment and also because patients will want to be screened for AEs related to INJ.) However, the statistical analysis will be by intent to treat (ITT) and will include all 194 randomized to treatment; patients who are lost to follow up prior to 3 months will be considered treatment failures. The number of patients we expect to be responders to each of the treatments at the 3-month assessment is based on the pivotal trials shown in Table 1. We separated them in this way in Figure 3 to be able to estimate the numbers of non-responders who are likely to choose an additional treatment option after 3 months. The expected number of non-responders eligible for an additional therapy at 3 months is 63 for the INJ arm^16 and 17 for the biofeedback arm^15. Assuming equal probability of choosing either of the 2 available options as an added or alternative treatment, we could expect 40 patients to choose the SNS treatment, 32 to choose BIO, and 9 to choose INJ. For the primary analyses of follow up at 6, 12 and 24 months, these non-responders will be retained in the ITT analysis as non-responders to their primary assignment at randomization. However, when we perform exploratory analyses of treatment combinations, these subjects will be treated as distinct groups and compared to patients who received monotherapy for the duration of the study. These comparisons (Aim D) are exploratory because there is insufficient power to test for significance. The left column of boxes in Figure 3 shows how we intend to follow up the responders to EMM.

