- C. Identify baseline predictors of responsiveness to each intervention and the mechanistic basis for each treatment. Candidate predictors are (a) demographic variables (e.g., sex, age, race, ethnicity, education); (b) clinical history variables (e.g., FI frequency, volume, duration, and association with urgency and diarrhea); and (c) baseline pelvic floor physiology (e.g., anal canal resting pressure, squeeze pressure, duration of squeeze, rectal sensory threshold for first sensation and urgency, maximum tolerable volume, structural integrity of anal sphincters assessed by ultrasound, and integrity of the pelvic floor innervation by trans-sacral and trans-lumbar magnetic evoked potentials).

- D. Evaluate treatment combinations. Patients who do not meet the responder criterion by 3 months follow up will be offered the option of choosing additional therapy. This constitutes a pragmatic clinical trial which mimics clinical practice and will provide preliminary data for a future study. A second reason for allowing patients to add an additional preferred treatment if they do not show at least a 75% improvement is to facilitate recruitment; in our feasibility survey, subjects told us that the opportunity to try another treatment if the first failed would increase their willingness to be randomized. Data analysis will estimate 95% confidence intervals for the percent of responders to each treatment combination and to each monotherapy, and differences in responder rates between groups will be assessed.
  - Research objective 4. To compare the improvement in FI after combination treatment versus monotherapy and compare improvement among various treatment combinations, up to 24 months after administration of each treatment combination, compared to monotherapy.
  - Research objective 5. To estimate differences in the magnitude of improvement in FI from baseline to end of treatment between the treatment combinations.
- E. Assess the efficacy and durability of enhanced medical treatment and identify patient characteristics that predict treatment response.
  - Research objective 6. To estimate the responder rate during the last two weeks of enhanced medical treatment and also during follow up at 3, 6, 12, and 24 months.
  - Research objective 7. To assess the proportion of patients reporting AEs of pelvic pain of grade II or higher, or SAEs requiring hospitalization, during all weeks of medical treatment.

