2.3. Expected impact of this FI comparative effectiveness trial: The proposed project will improve scientific knowledge, technical capability, and clinical practice as they relate to the treatment of FI. A critical barrier to progress in the treatment of FI is the lack of understanding regarding comparative effectiveness of currently approved treatment modalities and their pathophysiological basis. Our objectives are to address this significant gap in our knowledge by (1) comparing the effectiveness, safety, and cost of two treatments, BIO and INJ at 3, 6, 12, 18, and 24 months following the end of treatment; (2) identifying patient characteristics at baseline that predict response to each intervention; (3) investigating the mechanistic basis for treatment success by examining rectal sensory thresholds, rectal compliance, neurophysiological parameters, and stool consistency; (4) evaluating the response to treatment combinations selected by non-responders compared to the primary treatment assignment; and (5) assessing the rate of response to EMM, the durability of response, and patient characteristics that predict benefit from medical treatment. SNS will not be included as a randomized study treatment as it is a more invasive treatment and appears to negatively impact the willingness of patients to participant in the study. We will offer SNS to participants as an additional treatment choice when they are identified as non-responders to the randomized treatment at the 3-month follow-up assessment, thus allowing them the opportunity to choose as an additional treatment either SNS or the other intervention to which they were not initially randomized (either BIO or INJ). Participants who do not meet clinical criteria for receiving SNS, or who previously received and did not respond to SNS treatment will not be offered SNS as a treatment option at 3-month follow up.

When the aims of this project are achieved, the concepts, methods, technologies and treatments or preventive interventions related to the management of FI will be changed as a result of (1) development of a rational basis for recommending treatment with BIO or INJ; (2) demonstration of comparative effectiveness of each treatment modality; and (3) a new understanding of the effects of each treatment on bowel symptoms, and quality of life, especially regarding safety, tolerability, and adherence.

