  - INJ will include a preparation for treatment and a treatment visit. Preparation will include the use of enemas and minimal restrictions on food intake. Prophylactic antibiotics should be started on the day of the procedure, per the treatment SOP. On the day of the procedure, a physician will inject 1 ml of dextranomer into each of 4 quadrants of the rectum proximal to the dentate line. Ten seconds will be allowed to pass before the injection needle is withdrawn to minimize drainage of the dextranomer. The patient will be scheduled to return in 6 weeks for possible repeat injection of a second 4 ml of dextranomer. At this second appointment, if FI has improved by 75% or more compared to baseline, the patient will be continued without a second injection. However, if the rate of FI is greater than 75% of baseline, the patient will be offered a second injection of dextranomer.
- 4. Combination therapy: The primary assessment of efficacy is at 3 months following the first treatment visit completed, and patients who have not achieved at least a 75% reduction in FI frequency compared to baseline will be classified as treatment failures; they will be invited to choose either the treatment to which they were not randomized or SNS as an adjunctive treatment for the remaining months of the study. One reason for offering non-responders an opportunity to try an additional treatment is to increase the likelihood that patients will consent to be randomized despite possibly having a priori preferences for one of the two treatments. The assumption that this will increase willingness to be enrolled was confirmed in the pilot feasibility survey we performed in 187 patients with FI representing the clinical sites: 57% of patients reported that the ability to receive the treatment of their choice if the assigned treatment was not effective, was important to their willingness to be randomized. Moreover, the estimated 46% of patients who do add a second treatment after the 3 months primary assessment will enable us to collect exploratory data on the possible benefits of combining these treatments. (None of the two investigational treatments can be discontinued.) Thus, the patients

Figure 1. Study Design

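### Aim D sets 3-month non-responders who add a treatment against whole-study monotherapy patients, who on the plan's own flow are mostly 3-month responders (minor)

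*Combined protocol and SAP*

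**What the plan says.** Under Aim D (section 1.1), patients below the 75% criterion at 3 months "will be offered the option of choosing additional therapy". Responders are not offered it. Aim D then calls for confidence intervals for the percentage responding to each combination "and to each monotherapy, and differences in responder rates between groups will be assessed". Research objective 4 compares improvement after combination treatment "up to 24 months after administration of each treatment combination, compared to monotherapy".

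Section 5.4 names the comparator most clearly. In the exploratory analyses of combinations, "these subjects will be treated as distinct groups and compared to patients who received monotherapy for the duration of the study". It expects 17 biofeedback (BIO) and 63 injection (INJ) non-responders at 3 months and, with the two available options equally likely, "we could expect 40 patients to choose the SNS treatment, 32 to choose BIO, and 9 to choose INJ". The caveat is: "These comparisons (Aim D) are exploratory because there is insufficient power to test for significance".

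The analysis sections do less than the aims. Section 8.3 plans Wilson intervals for each treatment-order combination at 6, 12 and 24 months, compared descriptively. For the severity scale, section 8.2 estimates change from baseline at 6 to 24 months separately for 3-month responders in each arm and for non-responders by the combination they chose, without testing. The quality-of-life and PROMIS scales follow the same methods.

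**The concern.** Membership of the two sides of the contrast is decided by the outcome at 3 months. A patient enters a combination group only by failing the 75% criterion. A patient who meets it stays on monotherapy. The later responder rates of the two sides then differ largely because of how the sides were formed, whatever the added treatment does.

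Low power is a different problem. More patients would narrow the intervals around the same selected difference. The documents neither restrict the comparator to non-responders, nor adjust for 3-month status, nor warn against reading the difference as an effect of adding treatment.

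At stake is Research objective 4. Aim D is meant to supply preliminary data for a future study, and a deficit produced by selection could steer that study away from combinations.

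**Working it through.** **Reproducing the plan's flow (section 5.4; response rates from Table 3)**

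- BIO: 97 × 0.80 = 77.6, so 78 assessed; 78 × (1 − 0.78) = 17.2, so 17 non-responders and 78 − 17 = 61 responders.
- INJ: 97 × 0.95 = 92.2, so 92 assessed; 92 × (1 − 0.32) = 62.6, so 63 non-responders and 92 − 63 = 29 responders.
- Totals: 80 non-responders and 90 responders among 170 assessed. Lost before 3 months: 19 BIO + 5 INJ = 24.
- Choices at 50:50: SNS 80/2 = 40, BIO 63/2 = 31.5, INJ 17/2 = 8.5. These sum to 80; the printed 40, 32 and 9 sum to 81 through rounding. The flow thus gives every non-responder an added treatment.
- Section 3.0, item 4, refers to "the estimated 46% of patients who do add a second treatment after the 3 months primary assessment". The denominator is not stated. If it is the 170 assessed, 0.46 × 170 = 78 of the 80 eligible, which also implies near-complete uptake.

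**Composition of the monotherapy group**

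Let d be the share of non-responders who decline an added treatment. The flow implies d = 0; other values are assumptions. The responder share is 90/(90 + 80d), or 90/(114 + 80d) if the 24 early losses count as monotherapy.

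| d | Without early losses | With early losses |
|---|---|---|
| 0 | 90/90 = 100% | 90/114 = 79% |
| 10% | 90/98 = 92% | 90/122 = 74% |
| 25% | 90/110 = 82% | 90/134 = 67% |
| 50% | 90/130 = 69% | 90/154 = 58% |

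In the INJ arm alone, without early losses, the share at d = 50% is 29/(29 + 31.5) = 48%. The combination groups hold 0% responders in every row.

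**What the contrast would show if adding a treatment did nothing**

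The documents do not give the inputs needed. I assume that a share p = 70 to 90% of 3-month responders are still responders later, that a share r = 0 to 20% of non-responders respond later with or without an added treatment, and that d = 0 to 50%.

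Without early losses: combination minus monotherapy = r − (90p + 80dr)/(90 + 80d) = −90(p − r)/(90 + 80d).

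- Smallest deficit (p = 0.70, r = 0.20, d = 0.50): −45/130 = −35 points.
- Largest deficit (p = 0.90, r = 0, d = 0): −81/90 = −90 points.

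With the 24 early losses counted as permanent failures: r − (90p + 80dr)/(114 + 80d).

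- Smallest deficit: 0.20 − (63 + 8)/154 = −26 points.
- Largest deficit: −81/114 = −71 points.

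For the INJ comparator alone, without early losses, at the most favourable corner: 0.20 − (20.3 + 6.3)/60.5 = −24 points. A deficit remains even where responders are no longer the majority.

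**The case against.** The strongest reply is that section 8.3, which governs the analysis, contains no combination-versus-monotherapy test or model for responder rates. Aim D is called exploratory, and the text says openly that only non-responders may add a treatment. Section 8.2 labels its two sides as responders and non-responders. All of this is right, and it is why the point is minor. It does not remove the point, because Aim D, Research objective 4 and section 5.4 still promise a contrast, and a descriptive comparison of groups selected on outcome can mislead as a tested one can.

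A second reply is that Aim D's percentage responding to each monotherapy could mean an all-randomized estimate. Taken alone, that wording allows it. Section 5.4, however, specifies patients on monotherapy for the whole study.

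A third is that uptake, persistence and later response are assumed here. That stands: the point ranges illustrate the problem and do not predict results. The composition at full uptake rests on the plan's own figures.

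Some stronger inferences are not supported:

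- A reader might infer that combinations must look worse. They need not; an effective second treatment could reverse the sign. The contrast is uninterpretable in either direction.
- A reader might cite the expected-impact text in section 2.3, "evaluating the response to treatment combinations selected by non-responders compared to the primary treatment assignment", as the same error. It can be read as setting response to the combination against response to the first assignment.
- A reader might see a conflict between Research objective 4's 24 months and visits counted from the start of the randomized treatment. The wording is an upper bound, so there is no error.

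**Conclusion.** The concern holds. As written, the combination-versus-monotherapy contrast compares groups with no 3-month responders against a group that is all responders on the plan's followed flow, or 79% if early losses are counted. Pooled over arms, responders remain the majority (58% or more) with up to half of non-responders declining; in the INJ arm alone they do not (48%, without early losses). With no effect of adding treatment, the expected deficit is about 35 to 90 points, or 26 to 71 with early losses counted, under the stated assumptions. The contrast therefore cannot answer Research objective 4, and the power caveat does not cover the reason.

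The reach is limited. The primary 3-month analysis, the sample size and Research objective 5 (combination against combination) are not affected. Severity is minor, because the aim is exploratory and its planned analysis descriptive.

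**What to change.** Remove the combination-versus-monotherapy contrast from Aim D, Research objective 4 and section 5.4. State the objective as response by treatment-order combination within 3-month non-responders, using the Wilson intervals already planned in section 8.3 and labelled as uncontrolled. Report by arm how many non-responders declined an added treatment.

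If the contrast is kept, say in section 1.1, in section 5.4 and beside the responder/non-responder split in section 8.2 that the groups are selected on 3-month response and that differences between them will not be interpreted as an effect of adding treatment.

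The cost is a few sentences and one table of counts, with no new data. The downside is that Research objective 4 would yield no estimate of the effect of adding treatment. This design cannot give one, since its own flow expects no followed non-responders who stay on their first treatment alone.

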#### 5.5 Feasibility Survey

In Year 1 of the U34 planning grant, we conducted two feasibility surveys to inform us whether sufficient numbers of subjects would be willing to be randomized to a 3-arm treatment study. In the first survey, we recruited 164 individuals through an internet registry who reported experiencing FI at least twice each month. The anonymous internet survey gave brief descriptions of BIO, SNS, and INJ including published reports of their effectiveness, safety, and cost. These subjects were then asked to rate the effectiveness and safety of each treatment on a 0-10 scale from "definitely not" to "yes, definitely". They rated their willingness to undergo each treatment on a 0-10 scale from "definitely not" to "yes, definitely". The 164 respondents to this survey included 112 females (68% of total sample), average age was 43 years, and average FISS severity score was 8 with 119 (73%) scoring in the moderate to severe range of FI severity. When asked to rate their willingness to enroll in a study in which they would be randomly assigned to one of these three treatments, 32% rated their willingness as 8 or greater on the 0-10 scale. When asked about each treatment separately they were significantly more willing to try BIO than INJ, and significantly more willing to try INJ than SNS. They rated these three treatments as equally effective but BIO was perceived as significantly safer than INJ, and INJ was perceived as significantly safer than SNS. Concerns expressed about the safety of SNS included infection risk, use of electricity, and possible nerve damage.

The second feasibility survey was carried out in the 4 clinical settings where this study would take place. From 40 to 51 patients with established diagnoses of FI participated at each site (total n=187). The proportion who would be willing to be randomized with a confidence rating of at least 8/10 was 40%. Patients who were unwilling to be randomized to this three-arm study most commonly listed safety concerns (62%) or unequal costs as reasons for their reluctance to be randomized. The data from these two surveys suggest that approximately 32% to 40% of eligible patients would be willing to be randomized. This is consistent with our assumption (see Figure 3) that 1 in 3 patients screened will be eligible and willing to be randomized.

## 6.0 Details of Interventions

Detailed procedure manuals were developed for each intervention (including the conservative run-in treatment) by separate protocol committees and are given below in subsequent Appendices. Adherence to these treatment protocols will be monitored as detailed in the procedure manuals.

#### 6.1 Enhanced medical management

The key components of treatment are patient education about the basic physiological mechanisms

for defecation, diet and medication to normalize stool consistency, and pelvic floor exercises taught by printed instructions. This treatment will be tailored to the underlying bowel disturbance as evaluated by a 2-week baseline bowel diary and described Manual of Procedures.

We have previous experience with the design and testing of EMM. In an RCT of BIO, we developed a protocol for a conservative run-in prior to implementation of the BIO or pelvic floor exercise protocol. This conservative treatment protocol included educating patients about the basic physiology of continence and defecation by showing them videos of defecography examinations, teaching them to normalize stool consistency by adding fiber to their diet or taking antidiarrheal or laxative medications if needed, and teaching

them to use a daily symptom diary to chart their progress. By the end of this 4-week intervention, there was an average 60% reduction in frequency of FI, and 22% of patients reported adequate relief.

Subsequently, with the support of grant R01 HS018695 we enhanced the EMM protocol by giving it to a series of small groups of patients with FI and asking them for feedback on what they found helpful or difficult, and what suggestions they had for improvement. Then with the assistance of two consultants who were nurses with expertise on FI ([name] and [name]), we developed a pamphlet for explaining each step in the program to patients and a series of training videos to teach nurses how to provide this intervention. These data were adapted by [name] into a Standard Operating Procedure for EMM.

#### 6.2 BIO training

The BIO protocol developed for the PFDN by [name] and other experts on BIO for FI provided the foundation for the Biofeedback Manual of Procedures. An important feature of this BIO protocol is its ability to adapt to the individual patient's needs: The most common physiological deficits that cause FI are (1) weakness of the external anal sphincter, (2) loss of the ability to sense weak distentions of the rectum caused by the movement of stool into the rectum, and (3) strong urges associated with rectal contractions that overwhelm the patient's ability to retain stool in the rectum long enough to reach the toilet. We developed separate BIO procedures specific to each of these deficits: (1) strength training for sphincter weakness, (2) sensory discrimination training to improve the ability to detect weak rectal distentions, and (3) urge resistance training. Each component is described briefly below:

- a. Strength training: The patient is provided with visual feedback of anal canal pressure and rectal pressure, shown as two line tracings on a graph. The interventionist explains that the sphincter should be able to squeeze with enough strength to increase anal canal pressure to at least 100 mmHg. Then over a series of 20-second trials, the interventionist sets intermediate goals that are beyond the patient's average ability but which can be achieved at least 25% of the time. The interventionist sets a target line on the screen for the patient to aim for, and as performance improves, this target is moved up. Once the patient demonstrates improvement in the maximum anal canal squeeze pressure, the interventionist asks the patient to focus on the rectal balloon pressure and to avoid increases in rectal pressure when squeezing the external sphincter. Rectal pressure is caused by contraction of the abdominal wall muscles, which many patients are in the habit of doing although this actually increases the likelihood of FI. Lastly, when the patient is making progress on strengthening the sphincter squeeze and isolating it from inappropriate abdominal wall contractions, the interventionist will ask them to practice increasing the duration of their anal squeeze response by keeping the anal pressure tracing above the target pressure for progressively longer periods.
- b. Sensory training: No visual feedback is provided to the patient during sensory training; instead they are asked to focus on internal sensations to learn to recognize weaker distentions. The interventionist rapidly inflates the rectal balloon using a hand-held syringe and holds the air in the balloon for 5-seconds before withdrawing it. The patient is asked to squeeze when they feel any sensation in their rectum and to also report their perception verbally to the interventionist. The first distention is with 50 ml of air which most patients can detect. If the patient detected and responded to the 50 ml distention, the next distention is 10 ml less. This is repeated until the patient begins to make errors; the last distention to which they responded correctly is the sensory threshold. At this point the interventionist switches to a discrimination training protocol in which some distentions are at the sensory threshold and some 5 ml less than this with the sequence being made unpredictable to the patient. The interventionist provides verbal encouragement during training to help the patient gradually improve their sensory threshold.
- c. Urge resistance training: Some patients with FI have strong urge sensations associated with rectal contractions, and they are unable to make it to the toilet. These urge sensations may be precipitated by anxiety about the possibility of having an accident (commonly experienced when they are trying to open the door of their house after returning from a shopping trip). Urge resistance training is based on the principles of systematic desensitization of a feared situation. The interventionist first inflates the rectal balloon to

identify the threshold for a strong urge. She (or he) then deflates the rectal balloon by 30 ml to reduce the intensity of the urge sensation and has the patient use deep breathing to relax. She then re-inflates the rectal balloon slowly while encouraging the patient to use relaxation to inhibit the urge sensation. Three to four such ramp distentions are used in the training session. It is usually possible to see an improvement in the tolerance for rectal distention within a session.

Which of these three BIO protocols are used, alone or in combination, depends on the patient's deficits. To guide the BIO therapist, a brief anorectal manometry test to assess sphincter squeeze responses and sensory thresholds is performed at the beginning of each BIO session. The patient's symptom diary is also used to determine what type of training to focus on during BIO: the occurrence of FI without awareness suggests the need for sensory discrimination training while the occurrence of strong urges before FI suggests a need for urge resistance training. Strength training is provided in every BIO training session, but the interventionist may place greater emphasis on maximum squeeze, squeeze duration, or avoidance of abdominal wall contractions based on the initial anorectal manometry assessment.

BIO training and anorectal manometric testing will use the Medspira Anorectal Manometry system and MCompass software (Minneapolis, MN). The PFDN worked closely with software engineers at Medspira to tailor the software to the needs of BIO therapy and to incorporate on-screen prompts to assist the BIO interventionist in following the protocol.

We have also developed a program for training the BIO interventionists and monitoring their adherence to protocol. The key elements are these: (1) we recruit physical therapists or nurses with prior experience in muscle retraining, (2) these candidates are asked to review a series of training slides and videos and to pass built-in quizzes, and (3) they are trained one-on-one with a live patient surrogate and then evaluated (certified) with a live patient surrogate by [name].

*6.3 INJ of dextranomer:* This protocol is a modified version of the protocol used by Graf to ensure consistency across sites and safety of patients. Patients are treated prophylactically with oral antibiotics to minimize injection site infections. One ml of NASHA dextranomer is injected through an anoscope into each quadrant of the submucosa (4 ml total) approximately 5 mm above the dentate line. After each INJ, the needle is left in place for 10 seconds to avoid backward leakage of contrast through the injection channel. Following the INJ patients are counselled to use stool softeners (docusate sodium) until the first bowel movement and to use paracetamol as needed for INJ site discomfort. Prophylactic antibiotics will be administered for 2 days starting on the day of injection. Six weeks after initial INJ, patients return for evaluation, and if the patient has achieved less than 75% reduction in FI, a second INJ is given.

6.4 Comparison of elements of BIO and INJ:

Table 9 shows the elements of the two treatments compared to each	h other.
	rouior.

	Enhanced Medical Management	Biofeedback	Injection
Preparation	None	None	Diet restrictions; enemas; and antibiotics per the procedure SOP
Number of visits	2 visit + 2 phone calls	5-6 visits	2 visits
Visit duration	60 min 1 st visit; 15 min phone calls (Day 3; Day 14); 30 min last visit	60 min	45 min
Visit frequency	1 st and last visits (start of treatment and after treatment program has ended)	Up to 2 visits per week, spaced 2-10 days apart for first 5-6 weeks or so	0 and 6 weeks
Procedure	Daily sphincter exercises, meds to normalize bowel habits	Learn how to improve strength and rectal sensation	Bulking agent injected into rectal wall to narrow opening
Expected Adverse Events	None	None	Pain at injection site, bleeding, infection

